Diary Card – Subjects will be provided a Diary Card to record local reactions, systemic events, and oral temperature for the 7 days after the maintenance dose. If there are any events ongoing after Day 8, these events will be followed until resolution and the stop date recorded. The Investigator (or Subinvestigator) will review Diary Cards with the subject. Any changes or comments to the subject's Diary Card must be made on the Diary Card and initialed and dated by the Investigator (or Subinvestigator). The Diary Card **AND** the Investigator's (or Subinvestigator's) assessment will serve as the source document. A sample of the Diary Card is provided in [Appendix 3](#).

An event recorded on the Diary Card should not be recorded on the AE eCRF unless it meets the criteria of an SAE.

AEs (including SAEs, AESIs, and MAAEs) – refer to [Section 7](#).

AEIS – refer to [Appendix 4](#) for list.

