Appendix 3 Sample Diary Card

Please assess your symptoms and complete this form each evening (after 4 pm)

Day	Date	Oral Temp (°F)	Systemic Events							Local Reactions (at the Injection Site)				
			Headache (0 to 3)	Chills (0 to 3)	Fatigue (0 to 3)	Nausea (0 to 3)	Diarrhea (0 to 3)	Vomiting (0 to 3)	Muscle Aches (0 to 3)	Pain (0 to 3)	Tenderness (0 to 3)	Swelling (0 to 3)	Swelling (size, mm)	Redness (size, mm)
1														
2														
3														
4														
5														
6														
7														
8														

Instructions for Scoring Intensity

Intensity Grading Scale for Systemic Events
 
0 = None 1 = Mild, no interference with daily activity 2 = Moderate, some interference with daily activity 3 = Severe, significant interference, prevents daily activity
	
Intensity Grading Scale for Pain
 
0 = None 1 = Mild, awareness of pain but it does not interfere with daily activity and no pain medication is taken 2 = Moderate, awareness of pain and there is interference with daily activity or requires non-narcotic pain medication 3 = Severe, awareness of pain and it prevents daily activity or requires use of narcotic pain medication
	
Intensity Grading Scale for Tenderness
 
0 = None 1 = Mild, hurts to touch 2 = Moderate, hurts with movement 3 = Severe, significant discomfort at rest
	
Intensity Grading Scale for Swelling
 
0 = None 1 = Mild, does not interfere with daily activity 2 = Moderate, interferes with daily activity 3 = Severe, prevents daily activity

---	--	--	--

Instructions for Measuring Size: Use the ruler provided and record the number of millimeters across the widest part of the red/swelling area.

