## **12 SAFETY ANALYSES**

### **12.1 Reactogenicity**

Frequency counts will be presented for systemic events and local reactions for the safety population. This will be done for events occurring within the first 7 days following the maintenance dose. Results will be presented by treatment group and maximum severity. Duration, in days, of events will also be summarized with n, median, minimum and maximum. All analyses will be done for the safety population.

Antipyretic and analgesic medications taken within 7 days after the maintenance dose will also be summarized by treatment group.

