Any Local Reaction		n (x.x%)	n (x.x%)
Pain		n (x.x%)	n (x.x%)
ETC			

Program:

Date Produced: mm/dd/yy

Programming Notes:

- Information comes from the Diary Card
- If a subject has multiple of the same events, take the maximum severity.
- During the 7 day period after the (Days 1-7) a subject should only be counted one time. If a subject has a sign/symptom at least once during that 7 day interval the subject is counted for that sign/symptom.
- Watch page breaks. Please try and keep all the grades together for a sign/symptom.
- Do not include Grade=0 as Grades of 0 imply "None" or no event.
- Fever is based on Temperature (F) which is collected on the Diary Card. See Appendix 2 in the protocol for grade definitions. Grade 1 = 100.4-101.1; Grade 2 = 101.2-102.0; Grade 3 = 102.1-104; Grade 4 >104.

- For Redness (mm) and Swelling (mm), see also Appendix 2 in the protocol. For both redness and swelling: Grade 1 = 2.5-5 cm; Grade 2 = 5.1-10 cm; Grade 3 = >10cm; Grade 4 is Necrosis or exfoliative dermatitis, which we won't be able to determine and will be handled separately as an AE.

[Sponsor]

Protocol: [Protocol number]

page x of y

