**Table 14.3.1.8: Descriptive Summary of Duration (days) of Systemic Events and Local Reactions by Treatment**

Safety Population

Systemic Events and Local Reactions	Statistic	GEN-003 60 ug/ M2 50 ug N=xx	Placebo N=xx
Fever	N	xx	xx
	Median	xx.x	xx.x
	Minimum	xx	xx
	Maximum	xx	xx
Headache	N	xx	xx
	Median	xx.x	xx.x
	Minimum	xx	xx
	Maximum	xx	xx
Chills	N	xx	xx
	Median	xx.x	xx.x
	Minimum	xx	xx
	Maximum	xx	xx
Fatigue	N	xx	xx
	Median	xx.x	xx.x
	Minimum	xx	xx
	Maximum	xx	xx
Nausea	N	xx	xx
	Median	xx.x	xx.x
	Minimum	xx	xx
	Maximum	xx	xx
Dairrhea	N		
	Median		
ETC...	ETC...		

Program:

Date Produced: mm/dd/yy

Programming Notes:

- Information comes from the Diary Card
- For start date, use the date from when the symptom is first recorded on the card (severity >0). For the stop date, use the date when the symptom is last present on the card (severity > 0). If a stop date is not available, then this needs to be given to the CDM.

[Sponsor]

Protocol: [Protocol number]

page x of y

**Table 14.3.1.9: Summary of Antipyretic/Analgesic Medications Taken Within 7 Days after Maintenance Dose by Treatment Group, Drug Class and Preferred Term**

Safety Population

Preferred Term	GEN-003 60 ug/ M2 50 ug N=xx	Placebo N=xx
Any Anti-Fever/Anti-Pain Medication	n (x.x%)	n (x.x%)
Preferred Term 1	n (x.x%)	n (x.x%)
Preferred Term 2	n (x.x%)	n (x.x%)
Preferred Term 3	n (x.x%)	n (x.x%)
etc.		

Program:

Date Produced: mm/dd/yy

Programming Note:

- Antipyretic/analgesic medications are defined as medications with an ATC2 Class of 'ANALGESICS' or 'ANTIINFLAMMATORY AND ANTIRHEUMATIC PRODUCTS'

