**Listing 16.2.7.1: Systemic Events (Diary Card) by Subject**  
 Safety Population

Treatment	Subject Number	Visit	Date	Temperature (F)	Headache	Chills	Fatigue	Nausea	Etc.
GEN-003 60 ug / M2 50 ug	xxxx	Day 1 Pre	ddmmmyyyy	xx.x	0	0	0	0	
		Day 1 (1hr)			1	1	1	1	
		Day 1			2	2	2	2	
		Day 2			3	3	3	3	
		Day 3							
		Day 4							
		Day 5							
		Day 6							
		Day 7							
Placebo	xxxx								

Grade 0 = None; Grade 1 = Mild; Grade 2 = Moderate; Grade 3 = Severe  
 Program:

Date Produced: mm/dd/yy

Programming Notes:

- Sort by treatment, subject, and visit.
- Data comes from Body Symptoms-Reactions Log CRF; for visit and time information, use the variable DCNOMDAT.
- Diary Cards are filled out for the 7 days following the maintenance dose.
- Page break by subject.
- Always include the first 7 days after the maintenance dose; if additional days are captured and the symptoms are all = 0 (None), then do not present on listing.

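### Table 14.3.1.8 measures reaction duration from the first to the last symptomatic card day, so symptom-free days in between count as reaction days, mainly inflating the maximum and individual durations

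*SAP*

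**What the plan says.** SAP 12.1 (Reactogenicity) promises a duration summary: "Duration, in days, of events will also be summarized with n, median, minimum and maximum". The derivation stands only in the programming notes to Table 14.3.1.8. For the start: "For start date, use the date from when the symptom is first recorded on the card (severity >0"). For the stop: "For the stop date, use the date when the symptom is last present on the card (severity > 0"). The only exception covers a missing date: "If a stop date is not available, then this needs to be given to the CDM".

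The notes do not split separate episodes, remove days scored 0, or require the days between start and stop to be symptomatic. Protocol 10.9.1 asks for frequency and severity only, so it does not override the rule.

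Repeat episodes are foreseen next door. The notes to Table 14.3.1.7 say "If a subject has multiple of the same events, take the maximum severity". The duration table has no counterpart. The sample Diary Card (Protocol Appendix 3) scores most symptoms daily from 0 to 3, starting "0 = None 1 = Mild, no interference with daily activity", so symptom-free days are visible in the data.

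**The concern.** A span equals a duration only if the symptom is continuous. Headache, fatigue, nausea and muscle aches also occur for reasons unrelated to an injection. One later unrelated day can therefore stretch a short post-dose reaction across most of the card. This also happens to reactions that had already resolved, so it is a different matter from how reactions still ongoing after the card are closed.

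The safety objective (SAP 3.3) is safety and tolerability against placebo, and this is the SAP's only table of reaction duration. It reports four statistics, one of which is the maximum. A reader who sees a maximum of 7 days would take it as a week-long reaction, when the card may show two isolated days.

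**Working it through.** The plan states no figure to reproduce. The check applies the written rule to card patterns and compares it with a count of symptomatic days.

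**Inputs from the documents.** The start and stop rules are those quoted above. For card length, the SAP says "Diary Cards are filled out for the 7 days following the maintenance dose" (Listing 16.2.7.1) and the Table 14.3.1.7 notes use Days 1-7, so 7 days is the base case. The sample card has 8 rows, which is taken as a sensitivity case.

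**Assumptions, not in the documents.**
- Span = last symptomatic day − first symptomatic day + 1 (the SAP does not write the subtraction).
- Background symptoms occur with probability p on each day, independently.
- In the GEN-003 arm, 75% of subjects have an acute reaction of 1, 2 or 3 days (35%, 40%, 25%), starting on Day 1 or Day 2 with equal chance. Placebo has background only.

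**Worked case.** Symptom on Days 1 and 7 only: span = 7 − 1 + 1 = 7; symptomatic days = 2.

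**Placebo, share overstated.** A card is not overstated if its symptomatic days form one unbroken run. P(one run) = Σ (8 − L) p^L (1 − p)^(7 − L) over L = 1 to 7, and P(any symptom) = 1 − (1 − p)^7.
- p = 0.05: 0.2694 / 0.3017 = 0.893, so 10.7% are overstated.
- p = 0.10: 0.4110 / 0.5217 = 0.788, so 21.2% are overstated.

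**GEN-003, full 7-day span.** This needs a symptom on Day 1 and on Day 7. A reaction starting on Day 1 (0.75 × 0.5 = 0.375 of subjects) supplies Day 1; all others need background on both days. Share = (0.375p + 0.625p²) / (0.75 + 0.25[1 − (1 − p)^7]).
- p = 0.05: 0.0203 / 0.8254 = 2.5%.
- p = 0.10: 0.0438 / 0.8804 = 5.0%.

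**All patterns of a 7-day card, enumerated exactly, among subjects with the symptom.**

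| p per day | Overstated, GEN-003 | Overstated, placebo | 7-day span, GEN-003 | 7 counted days, GEN-003 | Median GEN-003, span / count | Median placebo, span / count |
|---|---|---|---|---|---|---|
| 5% | 16% | 11% | 2.5% | <0.01% | 2 / 2 | 1 / 1 |
| 10% | 29% | 21% | 5.0% | <0.01% | 2 / 2 | 1 / 1 |
| 15% | 40% | 31% | 7.6% | 0.01% | 3 / 2 | 1 / 1 |
| 20% | 49% | 41% | 10.6% | 0.04% | 4 / 3 | 2 / 2 |

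With an assumed 30 GEN-003 subjects having the symptom, the chance that at least one shows a 7-day span is 1 − (1 − 0.0246)^30 = 53% at p = 5% and 1 − (1 − 0.0497)^30 = 78% at p = 10%. By counted days it is below 0.1% in both cases.

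**Sensitivity.**
- 8-row card: overstated shares rise to 20% / 13% (GEN-003 / placebo) at 5% and 35% / 26% at 10%. At 10% the GEN-003 median becomes 3 against 2.
- Day-to-day correlation of 0.3, 7-day card: the shares fall to 11% / 7% and 21% / 14%. Medians are unchanged at both rates.
- All reactions starting on Day 1, or all on Day 2, 7-day card at 10%: the GEN-003 overstated share is 32% or 26%, and the 7-day-span share is 8.8% or 1.1%. The all-Day-1 case also moves the GEN-003 median to 3 against 2.

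**The case against.** The strongest reply concerns size. The table is descriptive and untested. The frequency and severity table, which carries what the protocol asks for, is unaffected. Listings 16.2.7.1 and 16.2.7.2 show daily scores, so gaps can be seen and durations recalculated. No decision in the documents uses duration. No passage gives a daily background rate or a distribution of reaction lengths, and correlation between days shrinks the effect. All of this stands, and it is why the point is minor.

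A second reply is that counting days is not clearly better. The unrelated headache on Day 7 still adds a day, so background stays mixed in. A blank card day inside a continuous reaction would drop out of a count, because SAP 5.5.1 allows no imputation, whereas the span bridges it. The first part stands as a limit on the remedy. The second is met by a blank-day rule.

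A reader might infer that the comparison between arms then reflects background frequency instead of the reaction. The documents do not support that. Placebo follows the same rule and its column shows the background. In the base case at 5% and 10% the medians are 2 and 1 under either definition. At an assumed 15% the gap widens by a day (3 and 1 against 2 and 1), because an early reaction anchors the start. That is reaction and background combined, not background replacing reaction.

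**Conclusion.** The point holds as a fault in a stated derivation rule: days scored 0 between episodes are reported as reaction days, and nothing elsewhere in the protocol or SAP corrects this. The maximum and individual durations are affected most. For background rates of 5% to 10% per day on a 7-day card, roughly one in six to three in ten GEN-003 subjects with the symptom, and one in nine to one in five placebo subjects with it, would have an overstated duration. These sizes rest on the assumed background rate, independence between days, and the assumed reaction pattern.

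It would go too far to say that the medians are generally distorted. In the base case they do not move at 10%, and the GEN-003 median shifts only between 10% and 15%; the shift at 10% needs the 8-row card or all reactions starting on Day 1. Means are not reported in this table, so inflation of the mean has no bearing on it. The consequence is a potentially misleading descriptive table, not a threat to any safety conclusion.

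**What to change.** Replace the start and stop notes to Table 14.3.1.8 with a definition along these lines: *Duration is the number of Diary Card days with severity above 0 (derived grade above 0 for fever and redness). A blank day counts as symptomatic only when flanked by symptomatic days. The first-to-last span is shown as a second row, labelled as such.*

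The wording on derived grade is needed because the card records fever as a temperature and redness in millimetres, so severity above 0 is undefined for them. The blank-day rule should be stated openly as an exception to SAP 5.5.1; SAP 11.1 already makes a similar exception for missing lesion-diary days flanked by positive entries.

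The cost is one programming note and one extra row per symptom, with no new data. The primary row may not match earlier GEN-003 tables if those used the span; the second row covers that. The count does not separate background symptoms from the reaction. It only stops symptom-free days being counted.

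Reactions still present at the end of the card are a separate matter. Protocol 6.1 says "If there are any events ongoing after Day 8, these events will be followed until resolution and the stop date recorded", and the card-based stop date in Table 14.3.1.8 must be reconciled with that.

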**Table 14.3.2.1: Frequency Table of Subjects with Serious Adverse Events by SOC, Preferred Term and Treatment**

Safety Population		
	GEN-003 60 ug/ M2 50 ug N=xx	Placebo N=xx
MedDRA SOC Preferred Term		
Total Number (%) of Subjects With a Serious AE	x (x.x)	x (x.x)
SOC1	x (x.x)	x (x.x)
PT1	x (x.x)	x (x.x)
PT2	x (x.x)	x (x.x)
---		
SOC2		
PT1	x (x.x)	x (x.x)
PT2	x (x.x)	x (x.x)
---		
-----		
SOCn		
PT1	x (x.x)	x (x.x)
PT2	x (x.x)	x (x.x)
---		

Note: Adverse event mapping was based on the MedDRA Version xx.x thesaurus.

Note: Subjects who have the same serious adverse event more than once are counted only once for the Preferred Term.

Subjects who have more than one serious adverse event within a System Organ Class are counted only once in that System Organ Class.

Program:

Date Produced: mm/dd/yy

[Sponsor]

Protocol: [Protocol number]

page x of y

**Table 14.3.2.2: Frequency Table of Subjects with Medically Attended Adverse Events by SOC, Preferred Term and Treatment**

Safety Population		
	GEN-003 60 ug/ M2 50 ug N=xx	Placebo N=xx
MedDRA SOC Preferred Term		
Total Number (%) of Subjects With a Medically Attended AE	x (x.x)	x (x.x)
SOC1	x (x.x)	x (x.x)
PT1	x (x.x)	x (x.x)
PT2	x (x.x)	x (x.x)
---		
SOC2		
PT1	x (x.x)	x (x.x)
PT2	x (x.x)	x (x.x)
---		
-----		
SOCn		
PT1	x (x.x)	x (x.x)
PT2	x (x.x)	x (x.x)
---		

Note: Adverse event mapping was based on the MedDRA Version xx.x thesaurus.

Note: Subjects who have the same medically attended adverse event more than once are counted only once for the Preferred Term. Subjects who have more than one medically attended adverse event within a System Organ Class are counted only once in that System Organ Class.

Program:

Date Produced: mm/dd/yy

**List of Statistical Listings for GEN-003-005**

Listing No.	Listing Title	Analysis Population
16.2.1	Subject Disposition and Reasons for Discontinuation From Study	Safety
16.2.2.1	Protocol Deviations by Subject	Safety
16.2.2.2	Randomization and Analysis Populations by Subject	Safety
16.2.3	Subjects Excluded from the Per Protocol Analysis Population	Safety
16.2.4.1	Baseline Demographics by Subject	Safety
16.2.4.2	Medical History by Subject	Safety
16.2.4.3	Prior Medications by Subject	Safety
16.2.4.4	Concomitant Medications by Subject	Safety
16.2.5.1	Dosing Status by Subject	Safety
16.2.5.2	Dosing Date/Time by Subject	Safety
16.2.6.1	Electronic Diary Data by Subject	Safety
16.2.6.2	EQ-5D-5L Data by Subject	Safety
16.2.7.1	Systemic Events (Diary Card) by Subject	Safety
16.2.7.2	Local Reactions (Diary Card) by Subject	Safety
16.2.7.3	Adverse Events by Subject	Safety
16.2.7.4	Serious Adverse Events by Subject	Safety
16.2.7.5	Adverse Events Associated with Discontinuation of Dosing by Subject	Safety
16.2.7.6	Adverse Events Leading to Death by Subject	Safety
16.2.7.7	Medically Attended Adverse Events by Subject	Safety
16.2.7.8	Adverse Events of Special Interest by Subject	Safety
16.2.8.1	Urine Pregnancy Test Results by Subject	Safety
16.2.8.2	Pregnancy Results by Subject	Safety

[Sponsor]

Protocol: [Protocol number]

page x of y

**Listing 16.2.1: Subject Disposition and Reasons for Discontinuation From Study**

Safety Population

Treatment	Subject Number	Subject Status	Disposition Date	Reason(s) for Discontinuation	Discontinuation Explanation
GEN-003 60 ug / M2 50 ug	xxxx		ddmmmyyyy	Completed	
	xxxx			Withdrew consent due to AE	
	xxxx			Withdrew consent not due to AE	
	xxxx			Lost to Follow-up	
				Non-compliance	
Placebo	xxxx			Investigator discretion	
	xxxx			Sponsor request	
	xxxx			Death	
	xxxx			Site termination	
	xxxx			Study termination	

Program:

Date Produced: mm/dd/yy

Programming Note

- "Subject Status": If DSDECOD = "Subject completed" then "Subject Status" = "Completed study". If DSDECOD is ≠ "Subject completed" then "Subject Status" = "Did not complete study".
- Sort by treatment, subject number.

**Listing 16.2.2.1: Protocol Deviations by Subject**  
 Safety Population

Treatment	Subject Number	Deviations Date	Deviation Type - Subject	Deviation Type - Site	Description of Deviation	Site Corrective Action
GEN-003 60 ug / M2 50 ug	xxxx	ddmmmyyyy	Subject did not meet eligibility criteria	Missed procedure		
		ddmmmyyyy	Subject received wrong treatment or incorrect dose	Out of window procedure		
		ddmmmyyyy	Subject received prohibited concomitant medication	Consent process error		
			Subject received a vaccine in excluded time period	Noncompliance		
			Subject used suppressive antiviral therapy	Other		
Placebo	xxxx		Consent process error			
	xxxx		Noncompliance			
	xxxx		Other			
	xxxx					
	xxxx					
	xxxx					
	xxxx					
	xxxx					
	xxxx					
	xxxx					

Program:

Date Produced: mm/dd/yy

Programming Note:

- Deviation information will come from the Protocol Deviations CRF.
- Sort by treatment, subject number, and deviations date.

[Sponsor]

Protocol: [Protocol number]

page x of y

**Listing 16.2.4.1: Baseline Demographics by Subject**  
Safety Population

Treatment	Subject Number	Age	Sex	Ethnicity	Race	Weight (lbs)
GEN-003 60 ug / M2 50 ug	xxxx			Hispanic	White	
	xxxx			Non-Hispanic	Black or African American	
	xxxx				Asian	
	xxxx				American Indian or Alaska Native	
	xxxx				Native Hawaiian or Other Pacific Islander	
Placebo	xxxx				Other, specify	
	xxxx					
	xxxx					

Program:

Date Produced: mm/dd/yy

Programming Notes:

- Data comes from the Eligibility-Demographics CRF.
- Sort by treatment, subject number.

[Sponsor]

Protocol: [Protocol number]

page x of y

**Listing 16.2.4.2: Medical History by Subject**  
Safety Population

Treatment	Subject Number	SOC	Preferred Term	Verbatim	Status
GEN-003 60 ug / M2 50 ug	xxxx				Ongoing
	xxxx				Intermittent
	xxxx				Resolved
Placebo	xxxx				
	xxxx				
	xxxx				

Program:

Date Produced: mm/dd/yy

Programming Notes:

- Sort by treatment, subject number, SOC and Preferred Term.

**Listing 16.2.4.3: Prior Medications by Subject**  
 Safety Population

Treatment	Subject Number	ATC Text Level 2/ Preferred Name/ Medication	Route	Start Date	Stop Date	Ongoing
GEN-003 60 ug / M2 50 ug	xxxx	XXXXXXXXXXXXX/ Pppppppppppppp/ mmmmmmmmmmmmmmmm	Oral	ddmmmyyyy	ddmmmyyyy	
	xxxx	XXXXXXXXXXXXX/ Pppppppppppppp/ mmmmmmmmmmmmmmmm	Topical			
	xxxx	XXXXXXXXXXXXX/ Pppppppppppppp/ mmmmmmmmmmmmmmmm	Subcutaneous			
		XXXXXXXXXXXXX/ Pppppppppppppp/ mmmmmmmmmmmmmmmm	Transdermal			
Placebo	xxxx	XXXXXXXXXXXXX/ Pppppppppppppp/ mmmmmmmmmmmmmmmm	Intraocular			
	xxxx	XXXXXXXXXXXXX/ Pppppppppppppp/ mmmmmmmmmmmmmmmm	Intramuscular			
	xxxx	XXXXXXXXXXXXX/ Pppppppppppppp/ mmmmmmmmmmmmmmmm	Inhalation			
		XXXXXXXXXXXXX/ Pppppppppppppp/ mmmmmmmmmmmmmmmm	Intraperitoneal			
	...	...	Nasal			
	xxxx	XXXXXXXXXXXXX/ Pppppppppppppp/ mmmmmmmmmmmmmmmm	Vaginal			

Program:  
 Programming Notes:

Date Produced: mm/dd/yy

- Sort by treatment, subject, start date, stop date, and medication.
- Prior meds are any meds with a start date BEFORE date of maintenance dose (Day 1).
- Prior Meds will be coded.
- Please try to keep subject data together. Depending on number of con meds per subject, this may not be possible.

[Sponsor]

Protocol: [Protocol number]

page x of y

**Listing 16.2.4.4: Concomitant Medications by Subject**  
Safety Population

Treatment	Subject Number	ATC Text Level 2/ Preferred Name/ Medication	Route	Start Date	Stop Date	Ongoing
GEN-003 60 ug / M2 50 ug	xxxx	XXXXXXXXXXXXX/ Pppppppppppppp/ mmmmmmmmmmmmmmmm	Oral	ddmmmyyyy	ddmmmyyyy	
	xxxx	XXXXXXXXXXXXX/ Pppppppppppppp/ mmmmmmmmmmmmmmmm	Topical			
	xxxx	XXXXXXXXXXXXX/ Pppppppppppppp/ mmmmmmmmmmmmmmmm	Subcutaneous			
		XXXXXXXXXXXXX/ Pppppppppppppp/ mmmmmmmmmmmmmmmm	Transdermal			
Placebo	xxxx	XXXXXXXXXXXXX/ Pppppppppppppp/ mmmmmmmmmmmmmmmm	Intraocular			
	xxxx	XXXXXXXXXXXXX/ Pppppppppppppp/ mmmmmmmmmmmmmmmm	Intramuscular			
	xxxx	XXXXXXXXXXXXX/ Pppppppppppppp/ mmmmmmmmmmmmmmmm	Inhalation			
		XXXXXXXXXXXXX/ Pppppppppppppp/ mmmmmmmmmmmmmmmm	Intraperitoneal			
	...	...	Nasal			
	xxxx	XXXXXXXXXXXXX/ Pppppppppppppp/ mmmmmmmmmmmmmmmm	Vaginal			

Program:

Date Produced: mm/dd/yy

Programming Notes:

- Sort by treatment, subject, start date, stop date, and medication.
- Concomitant meds are any meds which started on or after the date of maintenance dose (Day 1), or which started before date of maintenance dose and continued beyond date of maintenance dose.
- Concomitant Meds will be coded.
- Please try to keep subject data together. Depending on number of con meds per subject, this may not be possible.

[Sponsor]

Protocol: [Protocol number]

page x of y

